1.1 Overview

This study is a pilot project portion of an NIH Rare Disease Clinical Research Consortium focused on brain blood vessel malformations in three different rare diseases.

The focus of this specific project is on Sturge-Weber syndrome. Sturge-Weber syndrome is a rare, congenital syndrome with vascular malformations of the brain, skin, and eye. The underlying cause of SWS is unknown and the extent of involvement varies greatly from patient to patient. Those with brain involvement present with cognitive impairments, seizures, stroke-like episodes, and neurologic deficits, usually in infancy. Those with eye involvement frequently develop vision-threatening glaucoma and retinal injury. Treatment has been largely symptomatic and hampered by delayed diagnosis and the rarity of the condition.

2. Specific Aims (Hypothesis and Objectives)

We aim to gain a preliminary understanding of safety of sirolimus in Sturge-Weber syndrome and the feasibility of a trial to determine the impact of sirolimus upon cognitive impairments in Sturge-Weber syndrome. The primary objectives are 1) to assess for adverse events in this population and 2) determine best outcomes and biomarkers to be used as a treatment trial of cognitive impairments in Sturge-Weber syndrome. Through this effort, we will determine the feasibility and design for a succeeding randomized placebo-controlled trial, if justified by this trial. At the end of this trial subjects who want to will have the opportunity to enter the Extension Phase of the trial and continue on the study drug.

3. Background

Children living with Sturge-Weber syndrome (SWS) urgently need more effective medications. Many children develop a range of cognitive impairments, including intellectual disability, attention deficit disorder, learning disabilities, and autism. Classic SWS consists of a vascular birthmark on the face (capillary malformation), abnormal blood vessels in the eye (choroid hemangioma), and a vascular malformation in the brain (leptomeningeal angioma). In conjunction with their cognitive impairments, patients develop seizures and strokes, brain atrophy, hemiparesis, and vision deficits. Typical treatment includes anticonvulsants and low-dose aspirin. Stimulants are frequently used to treat attention issues and have demonstrated to be effective and tolerated in some patients with SWS (Lance, Lanier, Zabel, & [name], 2014). However, a recent review of a cohort of children at the Kennedy Krieger Institute treated with this approach reveals that cognitive impairments are common and only about 1/3 of patients have an IQ in the normal range (Kavanaugh et al., 2015). The PI3K/AKT/mTOR pathway, known for its essential regulatory functions in vascular growth and

organization, has previously been shown to be activated in capillary malformations associated with SWS (Shirazi et al., 2007). More recently, a sporadic R183Q mutation in GNAQ was identified at the Kennedy Krieger Institute (KKI) as the etiology of isolated capillary malformations and of SWS, further implicating this pathway, and thereby suggesting a potential therapeutic target (Shirley et al., 2013). The R183Q somatic mosaic mutation in GNAQ is predicted to hyperactivate the P13K/AKT/mTOR pathways.

Sirolimus has been used to treat individuals ages 0-31 years with complicated vascular anomalies as part of a Phase II clinical trial at Cincinnati Children's Hospital Medical Center (CCHMC). In that trial, sirolimus was safe even in the youngest cohort of patients, and pharmacokinetic studies were performed by [name] to elucidate appropriate dosing for patients based on age and goal drug level. While patients with Sturge-Weber syndrome were not eligible for that study, sirolimus has been tried for compassionate use in a teenage boy with Sturge-Weber syndrome, suffering from poorly controlled seizures with no significant toxicity (personal communication, [name]) and in an infant with CLOVES syndrome and hemimegencephaly, including vascular leptomeningeal enhancement consistent with early angiomatous changes, for his poorly controlled seizures (personal communication, [name]). In addition, a small clinical trial of 25 patients ages 2-18 has recently opened at Baylor using the mTOR inhibitor everolimus to treat refractory seizures in Sturge-Weber syndrome.

Furthermore, sirolimus has been studied in multiple clinical trials for the treatment of cognitive impairments and seizures in tuberous sclerosis. In modeling this trial after the trial studying the impact of sirolimus upon cognition in tuberous sclerosis complex (TSC), we aim to determine the impact of sirolimus upon cognition in Sturge-Weber syndrome. The primary objective of this pilot study is to determine the tolerability of sirolimus as an adjunct treatment in children and adults with Sturge-Weber syndrome related cognitive impairments. Sirolimus is FDA-approved for organ rejection in kidney transplants for individuals ≥ 13 years old. Additionally, sirolimus is FDA-approved as a prescription medicine used to treat lymphangioleiomyomatosis (LAM), a rare progressive lung disease that affects predominantly women of childbearing age. Therefore, this study is a pilot trial of a clinically available medication for an indication (cognitive impairments in Sturge-Weber syndrome) which does not currently have FDA approval. The line of research represented by this particular pilot study is novel with respect to the specific disease state under study (SWS), but is modeled after earlier research utilizing the same compound in a different disease (TSC). Both diseases have constitutive activation of the mTOR pathway.

4. Study Design and Methods

4.1 Inclusion Criteria

Patients with Sturge-Weber syndrome brain involvement as defined on neuroimaging (n=10 subjects, male and female, ages 3 to 31 years) and the following:

- 1. Male or female patients ages 3 to 31 years of age.
- 2. Cognitive impairment as defined by the following:
 - SWS cognitive neuroscore of ≥ 1
- 3. Ability to participate in direct neuropsychological and developmental testing.
- 4. English as primary language.
- 5. Stable anti-epileptic drugs (no changes in medications except dose for >3 months).
- 6. Adequate renal function. GFR must be greater than 50 ml/min/m2 as determined by the Schwartz Formula for children and MDRD for adults: http://www.nkdep.nih.gov/professionals/gfr calculators/index.htm
- 7. If female and of child bearing potential, documentation of a negative pregnancy test prior to enrollment determined by a urine test is required. Sexually active pre-menopausal female patients (and female partners of male patients) must use adequate contraceptive measures, excluding estrogen containing contraceptives, while on the study drug. Abstinence will be considered an adequate contraceptive measure.
- 8. INR ≤1.5 (Anticoagulation is allowed if target INR ≤ 1.5 on a stable dose of warfarin or on a stable dose of LMW heparin for >2 weeks.)
- 9. Adequate liver function as shown by:
 - Serum bilirubin ≤ 1.5x ULN
 - ALT and AST ≤ 2.5x ULN
- 10. Written informed consent according to local guidelines. Local guidelines for subject assent will also be followed.
- 11. Stable dose of medications affecting the cytochrome P-450 3A4 (CYP3A4) and p-glycoprotein (P-gp) systems for at least 3 months prior to consent.

4.2 Exclusion Criteria

- 1. Allergy to sirolimus or other rapamycin analogues.
- 2. Patients with seizures secondary to metabolic, toxic, infectious or psychogenic disorder, drug abuse or current seizures related to an acute medical illness.
- 3. Inability to keep follow-up appointments, maintain close contact with Principal Investigators, and/or complete all necessary studies to maintain safety.

- 4. Patients in need of immediate major surgical intervention.
- 5. Concurrent severe and/or uncontrolled medical disease, which could compromise participation in the pilot study (e.g. uncontrolled diabetes, uncontrolled hypertension, severe infection, severe malnutrition, chronic liver or renal disease, active upper GI tract ulceration, impaired or restrictive pulmonary function, pneumonitis or pulmonary infiltrates).
- 6. Chronic treatment with systemic steroids or another immunosuppressive agent. Patients with endocrine deficiencies are allowed to receive physiologic or stress doses of steroids if necessary. Inhaled steroids are allowed.
- 7. Known history of HIV seropositivity or known immunodeficiency. Testing is not required unless a condition is suspected.
- 8. Impairment of gastrointestinal function or gastrointestinal disease that may significantly alter the absorption of sirolimus (e.g. ulcerative disease, uncontrolled nausea, vomiting, diarrhea, malabsorption syndrome or small bowel resection). A gastric tube or nasogastric tube is allowed.
- 9. Patients with an active, bleeding diathesis.
- 10. Patients with uncontrolled hyperlipidemia: fasting serum cholesterol > 300 mg/dL AND fasting triglycerides > 2.5 x ULN.
- 11. Patients who have had a major surgery or significant traumatic injury within four weeks of study entry. Patients who have not recovered from the side effects of any major surgery (defined as requiring general anesthesia) or patients that may require major surgery during the course of the pilot study.
- 12. Patients with a prior history of organ transplant.
- 13. Patients who have received live attenuated vaccines within one week of start of sirolimus and during the pilot study.
- 14. Patients who have a history of malignancy.
- 15. Patients who are currently part of or have participated in any clinical investigation with an investigational drug within one month prior to enrollment.
- 16. Patients being treated with felbamate, unless treatment has been continuous for ≥ one year.
- 17. Patients currently receiving anticancer therapies or who have received anticancer

therapies within four weeks of study entry (including chemotherapy, radiation therapy, antibody based therapy, etc.).

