Sample Size: 10 (not including subjects screened or early withdrawals within first 2 months on study drug) Recruitment goal of five subjects from the Kennedy Krieger Institute and five subjects from Cincinnati Children's Hospital Medical Center. If Cincinnati
study drug) Recruitment goal of five subjects from the Kennedy Krieger Institute and five subjects from Cincinnati Children's Hospital Medical Center. If Cincinnati
Recruitment goal of five subjects from the Kennedy Krieger Institute and five subjects from Cincinnati Children's Hospital Medical Center. If Cincinnati
subjects from Cincinnati Children's Hospital Medical Center. If Cincinnati
I ('mildren's Riedical i enter (L') 'HRR(') is unable to meet their recruitment doal
then Kennedy Krieger Institute (KKI) may enroll additional participants to meet
the overall sample size of 10.
Target Enrollment October 1, 2016 – December 1, 2018 Period:
Primary Study 1) To gain a preliminary understanding of the safety and 2) determine best
Objective: outcomes to be used to assess the utility of sirolimus for the treatment of
cognitive impairments in Sturge-Weber syndrome (feasibility of full-scale
research design)
Study Population Patients with Sturge-Weber syndrome brain involvement as defined on
and Main Eligibility/ neuroimaging (n=10 subjects, male and female, ages 3 to 31 years) and the
Exclusion Criteria: following:
A A
1. Male or female patients ages 3 to 31 years of age.
Cognitive impairment as defined by the following:
 SWS cognitive neuroscore of ≥ 1
Ability to participate in direct neuropsychological and developmental
testing.
4. English as primary language.
5. Stable anti-epileptic drugs (no changes in medications except dose for
>3 months).
6. Adequate renal function. GFR must be greater than 50 ml/min/m2 as
determined by the Schwartz Formula for children and MDRD for adults:
 http://www.nkdep.nih.gov/professionals/gfr_calculators/i
ndex.htm
7. If female and of child bearing potential, documentation of a negative
pregnancy test prior to enrollment determined by a urine test is required.
Sexually active pre-menopausal female patients (and female partners of
male patients) must use adequate contraceptive measures, excluding
estrogen containing contraceptives, while on the study drug. Abstinence
will be considered an adequate contraceptive measure.
Q IND <1 ⊑ / Anticonggulation in allowed it towns thiD < 1 ⊑ an a stable data
8. INR ≤1.5 (Anticoagulation is allowed if target INR ≤ 1.5 on a stable dose

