Results of the above tests will be compared to age normed values. In addition, the difference in results between final test results and initial test results will be obtained for the cognitive functioning score of each subject. Mean and standard deviation of this difference for all 10 subjects will be calculated. These results will be used to determine whether individuals and the group as a whole demonstrated age normed changes in their cognitive functioning over the course of the six month trial. Neuropsychological testing will occur at both sites, KKI and CCHMC, and the deidentified results will be sent to KKI for analysis. There is no control group in this study of subjects who are not receiving study drug. The published test-retest standard deviations will be used to determine whether changes in testing results exceed expected test-retest changes in results.

Expected seizure rate can vary greatly both between subjects and for an individual. Subjects must be on the same AEDs for the past three months to join the study. Subjects whose seizures increase to the point where it is necessary to add another seizure medication, start the ketogenic or Atkins diet, or go for surgery to control their seizures will be removed from the study.

Quantitative EEG: An EEG will be done prior to starting study drug and at the end of the study while still on study drug. An asymmetry in power (roughly an integration of amplitude and frequency) in the affected side of the brain compared to the unaffected (or less affected) side of the brain, will be quantified as previously described (Hatfield et al., 2007; Ewen et al., 2009) for the quantitative EEG analysis. EEGs will occur at both sites, KKI and CCHMC, and the de-identified EEGs will be sent to KKI for analysis. The reason for this analysis is as a non-invasive biomarker of brain function which could be useful to develop as a marker of drug response. Quantitative EEG power analysis reflects an integration of the EEG activity amplitude and frequency. Therefore asymmetry of power on qEEG for these subjects reflects the increased slowing and decreased amplitude frequently seen in these patients interictally as their neurologic involvement progresses. Even patients with bilateral brain involvement have more involvement on one side than on the other side. Power asymmetry on qEEG has been shown to correlate with brain perfusion, brain atrophy, and SWS neuroscore, therefore, it has the potential as a biomarker responsive to

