Hyperlipidemia has been reported as an AE in of patients treated with sirolimus; however, at the low dose being used in this study this is not expected to be seen. As per the recent American Heart Association Scientific Statement on Cardiovascular Risk Reduction in High Risk Pediatric Patients, Tier III (65) management of hyperlipidemia should occur for patients with a fasting LDL cholesterol > 160 mg/dL.

Table 1

Event	Action				
Hyperlipidemia	Hyperlipidemia				
Fasting LDL >160 mg/dL and Patient ≥ 10 years old	 Diet (Nutritionist counseling – 30% of calories from fat, avoidance of trans-fats for six months) and exercise – Repeat Fasting LDL in three months. If fasting LDL cholesterol is still >160 mg/dL, continue diet and exercise and initiate a triglyceride-lowering 				

	agent such as an HMG-CoA reductase inhibitor (pravastatin, atorvastatin, or fluvastatin). Patients should avoid drugs that inhibit or induce CYP3A4. Patients should be monitored clinically and through serum biochemistry for the development of rhabdomyolysis and other AEs as required in the product data sheets for HMG-CoA reductase inhibitors. Continue to follow lipid panel every 8-12 weeks and adjust statins as necessary. • If after three months at this new target goal fasting LDL cholesterol is still >160 mg/dL, then the patient must be removed from protocol therapy.
Fasting LDL >160mg/dL and Patient <10 years old	 Diet (Nutritionist Counseling <30% of calories from fat, avoidance of trans-fats for six months). Repeat Fasting LDL in three months. If fasting LDL cholesterol is still >160mg/dL, continue diet and exercise and consider cholestyramine resin. If after three additional months at this new target goal fasting LDL cholesterol is still >160 mg/dL, then the patient must be removed from protocol therapy.
Triglycerides	
150-699 mg/dL	 Nutritionist counseling for low simple-carbohydrate, low-fat diet. If triglycerides remain < 700mg/dL, sirolimus therapy may continue at current dose target.

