≥ 700 – 1000 mg/dL	 Diet (nutritionist counseling) and exercise. Repeat lab work in three months. If patient is ≥ 10 years old and fasting triglycerides still ≥ 700 mg/dL and HDL is low, the patient should continue diet and exercise and consider fibrate or niacin cholestyramine resin. If after three months at this new target goal fasting triglycerides are still ≥ 700 mg/dL, then the patient must be removed from protocol therapy. If patient is < 10 years old and fasting triglycerides are still ≥ 700 mg/dL or patient cannot tolerate medical intervention, then sirolimus should be discontinued.

Toxicities Requiring Removal from Therapy:

Serious toxicities are not expected because a very low dose range is being used in this pilot study. If subjects experience any of the following toxicities regardless of

relationship to sirolimus or current trough level, they will be removed from protocol therapy.

Table 2

able 2				
Toxicity	Criteria for Removal			
Renal Function	If serum creatinine persistently increases (documented on at least two consecutive lab evaluations) to greater than 1.5X the baseline serum creatinine at trial entry, a creatinine clearance or GFR should be obtained. If the creatinine clearance or GFR is <70% of normal for age, regardless of attribution, the patient will be removed from protocol therapy.			
Infection	Patients who develop a ≥ Grade 3 pneumocystis carinii pneumonia or systemic fungal infection, regardless of attribution, will be removed from protocol therapy.			
Malignancy	Patients who develop lymphoma or other cancers, regardless of attribution, will be removed from protocol therapy.			
Pneumonitis	Patients who develop ≥Grade 2 sirolimus-related pneumonitis (symptomatic, but no intervention/oxygen therapy needed) will be removed from protocol therapy.			
Hypertension	Patients who develop sirolimus-related >Grade 3 hypertension will be removed from protocol therapy.			
Allergic Reaction	Patients who develop sirolimus-related >Grade 3 allergic reaction will be removed from protocol therapy.			
Rash	Patients who develop sirolimus-related Grade 4 rash will be removed from protocol therapy.			
Hyperlipidemia	Hyperlipidemia (with LDL cholesterol ≥160 mg/dL) not responsive to diet, exercise, and medical intervention for patients after three months (see Table 1 above), regardless of attribution, will be removed from protocol therapy.			

Drug Information:

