Vaccination - Immunosuppressants may affect response to the vaccination. Therefore, during treatment with sirolimus, vaccination may be less effective. The use of live vaccines should be avoided; live vaccines may include, but are not limited to, the following: measles, mumps, rubella, oral polio, BCG, yellow fever, varicella, and TY21a typhoid.

Toxicity: We do not expect any serious side effects with the low dose selected for this pilot study. The table below describes toxicities which have been reported for sirolimus over a wide dose range (up to 24 mg/m2 or higher).

Table 3

Table 3					
113	Common	Occasional	Rare		
1	Happens to 21-100	Happens to 5-20	Happens to < 5 children		
	children	children out	out of		
5	out of every 100	of every 100	every 100		
lmmediate:	Headache (L),	Chest pain, insomnia,	Hypotension, asthma,		
Within 1-2 days	hypertension (L),	dysphagia, vomiting,	increased cough,		
of receiving drug	nausea,	dyspnea	flu like syndrome,		
h.	immunosuppression	* *	tachycardia, anorexia,		
1	(L), diarrhea,		sensitivity reactions		
	constipation, fever		1		
	ol va				

Prompt: Within 2-3 weeks, prior to the next course	creatinine/BUN, anemia, asthenia, pain (abdominal, back, pain), hyperlipidemia, hypercholesteremia, hypertriglyceridemia,	leukopenia, hyper/hypokalemia (L), hypophosphatemia, rash, hives, pruritis, hyperuricemia, delayed wound healing, hypomagnesaemia (L)	Gastritis, esophagitis, flatulence, CNS abnormalities: (confusion (L), somnolence (L), depression (L), anxiety, anxiousness, paresthesias, emotional labiality, hypo/hypertonia, dizziness, neuropathy, hypesthesia, nervousness), infections (bacterial, fungal, viral—sepsis, cellulitis, herpes simplex & zoster, EBV, mycobacterial, sinusitis, pharyngitis, abscess, pneumonia, bronchitis, peritonitis), pleural effusions, pleural edema, hypoxia, thrombosis, thrombophlebitis, myalgia
Delayed: Any time later during therapy, excluding the above conditions	Acne		Skin ulcer, hirsutism (hypertrichosis) (L), gingival hyperplasia, abnormal vision, ear pain, cataracts, otitis, tinnitus, hemorrhage, ileus, chronic renal dysfunction, renal tubular necrosis, post-transplant diabetes mellitus (L), CHF, ascites, thrombocytopenic purpura (hemolyticuremic syndrome), arthrosis, bone necrosis, osteoporosis
Late: Any time after completion of treatment			Lymphoproliferative disorders, skin malignancies

Unknown	Sirolimus was embryo/feto-toxic in rats at dosages of 0.1 mg/kg and

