- A pharmacokinetic study will be done at the baseline visit. The subject will be started on a dose based on the recommended starting dose of mg/m2. The PK study results will be used to adjust their dose in order to get the patient to 4-6 ng/mL serum levels as quickly as possible. Subjects will be started on the study drug at study Visit 2. The PK results will be ready by study Visit 3 and the dose can therefore be adjusted. There will be no dose escalation. The dose will only change as indicated by the PK study or if the concentration of sirolimus is outside of the 4-6 ng/mL goal. The maximum dose will be 2 mg/day. If at the maximal dose, the sirolimus serum level is below the target level of 4-6 ng/ml, this result could impact the interpretation of the results if this subject has less of a response than other subjects. If it were to be the case that the majority of subjects are not able to reach this target range, then this trial will begin to evaluate safety and clinical trial measures for a lower than expected dose range of sirolimus as a treatment for cognitive impairments in Sturge-Weber syndrome. Furthermore, for each of the outcome measures we will plot the outcome versus serum level of the study drug. If there is a positive correlation between outcome and response, then this data would be used to select an optimal dose range to target in future trials.

The starting dose/m2 varies based on age and dosing strategy (often better tolerated when divided BID). Since our patients will be >3y, the starting dose should be 0.6mg/m2 q12h. We routinely do "miniPK" determinations using time 0, 1hour, and 3h post dose blood levels of sirolimus. Since with first dose the time 0 is 0, we will only draw the 1h and 3h levels. [name] at Cincinnati has an extensive background and multiple publications in this area and will do the PK analyses. While age-specific guidelines are usually appropriate to get to goal within 1 month, these patients may be on multiple anti-epileptics, some of which alter sirolimus metabolism. Most often, the metabolism is increased, meaning that levels decrease and patients who are "fully induced" for this particular CYP are likely to need 50% or more higher dosing than patients who are not on anti-epileptics. Subsequent levels will be trough levels done before their morning dose.

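### Exclusion 10 needs both lipids to be high, so a subject can start sirolimus with triglycerides already at or above Table 1's 700 mg/dL level: a minor, low-frequency safety gap

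*Combined protocol and SAP*

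**What the plan says.** **Entry.** Exclusion 10 (section 4.2) defines uncontrolled hyperlipidemia as "fasting serum cholesterol > 300 mg/dL AND fasting triglycerides > 2.5 x ULN". No other criterion in 4.1 or 4.2 sets a triglyceride ceiling. Exclusion 5 covers serious or poorly controlled illness at the investigator's discretion, and lipids are not among its examples.

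**Management on drug.** In section 5.3, Table 1, the row for 150 to 699 mg/dL says: "If triglycerides remain < 700mg/dL, sirolimus therapy may continue at current dose target". The row for 700 to 1000 mg/dL prescribes diet and exercise and then: "Repeat lab work in three months". Patients aged 10 or over have a second three-month step before removal. Where the patient "is < 10 years old and fasting triglycerides are still ≥ 700 mg/dL or patient cannot tolerate medical intervention, then sirolimus should be discontinued", the row gives the rule for younger children. As printed, Table 1 has no triglyceride row above 1000 mg/dL.

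**Timing.** Section 5.3 states: "Subjects will be started on the study drug at study Visit 2". The schedule in 4.6 puts Visit 2 at week 0. It lists a lipid profile at every visit, but EEG and neuropsychological testing only at baseline and at Visit 6 (week 26).

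**Counting and analysis.** The synopsis sets the sample size at 10, "not including subjects screened or early withdrawals within first 2 months on study drug". Section 5.7 likewise replaces only withdrawals in the first two months on drug. For the cognitive outcome the synopsis says: "Mean and standard deviation of this difference for all 10 subjects will be calculated". Section 5.7 specifies ending assessments only for loss of seizure control. For other removals it promises an effort to hold a final visit, without saying what is tested.

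**The concern.** The entry rule and the on-treatment rule use different logic. Entry takes two high values together to exclude. Table 1 acts on triglycerides alone. A subject can therefore receive a first dose while already in the range that the protocol manages as an on-treatment problem.

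The safety question comes first. Table 3 puts "hyperlipidemia, hypercholesteremia, hypertriglyceridemia" in its common column, though over a wide dose range, and section 5.3 does not expect hyperlipidemia at the dose used here. The sirolimus-related toxicity rules in 5.3 turn on attribution to the drug, so they do not clearly cover a value that predates it.

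The data question is secondary. A child under 10 who stays at 700 mg/dL or more may stop drug too late to be replaced and too early for the six-month test. A screen failure would not have used one of the 10 places.

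**Working it through.** The plan has no computed figure to reproduce. Section 6 says that 10 subjects were chosen on availability and experience. The check is therefore logic and calendar arithmetic.

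**1. Who passes exclusion 10.** Excluded = (cholesterol > 300) and (triglycerides > 2.5 × ULN). The ULN is not given, so it is assumed here.

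- 2.5 × ULN is 250 mg/dL at ULN 100, 375 at ULN 150 and 500 at ULN 200.
- A value of 700 exceeds 2.5 × ULN for any ULN below 700 / 2.5 = 280. Below that ULN, only the cholesterol half of the rule lets the subject in.
- Cholesterol/triglyceride pairs of 250/700, 300/750 and 290/1000 mg/dL all pass at ULN 100, 150 or 200. A pair of 301/800 is excluded.

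**2. When the three-month recheck falls.** One month = 365.25 / 12 / 7 = 4.35 weeks, so two months = 8.7 weeks and three months = 13.0 weeks. For a high value before or at first dose:

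| Clock starts | Recheck due | Scheduled visit |
|---|---|---|
| week -4 (early edge of screening window) | week 9.0 | week 14 |
| week -2 (screening) | week 11.0 | week 14 |
| week 0 (Visit 2) | week 13.0 | week 14 |

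All three due dates are after week 8.7, when replacement closes, and before week 26. A clock started by a value at week 2 or 5 would give week 15.0 or 18.0, which lie in the same interval.

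**3. The other reading of the under-10 rule.** That sentence is printed after the second three-month step and mentions intolerance of medical intervention. If the word *still* refers to the second recheck, stopping falls at 2 × 13.0 = about 26 weeks from week 0, or about 24 weeks from screening. That is close to the endpoint visit. The same two-step timing applies to patients aged 10 or over, so the data-loss argument does not reach them.

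**4. Size per case.** One of 10 planned six-month scores is 10%. With the same SD, the standard error of the mean change rises by √(10/9) = 1.054, or 5.4%. This is the arithmetic of any single dropout.

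**5. How fast an ending assessment goes off drug.** Section 5.3 gives a half-life of 79 hours with normal hepatic function. The fraction of the level left is 0.5^(72/79) = 53% at 3 days and 0.5^(168/79) = 23% at 7 days. The time since last dose therefore needs recording.

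**The case against.** The strongest reply is that Table 1 tolerates this state. At 700 to 1000 mg/dL it neither holds nor reduces sirolimus; it gives dietary measures and a recheck while dosing goes on. Starting a subject at 750 is then no worse than what the protocol accepts on drug, and the capitalised AND may be a deliberate permissive choice in a rare disease. Lipids are also measured at weeks 2 and 5, every visit has a continue-or-remove check, and section 7 allows stopping in the subject's interest. A withdrawal at week 2 or 5 would still be replaced.

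Much of this stands. A reader might infer that the protocol starts drug in someone who already meets a stopping rule. It does not, because 700 mg/dL triggers management and not removal. A reader might also infer that a child under 10 must stop at week 14. That is the natural reading of Table 1 but not the only one. Nor is the lost score peculiar to exclusion 10: any removal between month 2 and week 26 has the same effect. Table 1 says that sirolimus is discontinued, so an off-drug test at week 26 is not ruled out, and section 5.7 keeps data acquired before termination.

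What does not stand is reliance on the safeguards. Repeating the eligibility check reapplies the same AND, and exclusion 5 permits exclusion but does not require it. Tolerating a rise in a subject already on treatment is also different from choosing to start drug at that level.

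**Conclusion.** The point holds as a minor safety gap at entry. Exclusion 10 admits a subject with cholesterol of 300 mg/dL or less at any triglyceride value, including 700 mg/dL or more. As printed, it even admits a value above 1000 mg/dL, where Table 1 shows no action. Because the table is split in the text available, the missing row should be checked against the source; the point does not depend on it.

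The frequency is an assumption: probably 0 to 1 of 10. The documents give neither lipid prevalence nor the expected number of children aged 3 to 9. The data consequence also requires that the child stays at 700 or more, that no discretionary check intervenes, and that the earlier reading of Table 1 applies. It is then one on-drug six-month score, in a descriptive mean and SD. The documents do not support describing this as a threat to the trial's cognitive result.

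**What to change.** 1. **Exclusion 10.** Keep the present rule and add: *or fasting triglycerides ≥700 mg/dL on the most recent result available before first dose (Visit 1, or Visit 2 if available); may be rescreened once below 700*. The lipid profile is already scheduled at both visits. Replacing AND by OR would go further than needed: at an assumed ULN of 150 it would exclude from just above 375 mg/dL, where Table 1 lets therapy continue. The cost is a rare extra screen failure, which uses no place among the 10.

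2. **Section 5.7.** Extend the ending assessments (neuropsychological tests and EEG), now required for loss of seizure control, to every subject removed from drug before week 26 who has not withdrawn consent. Record days since last dose, and report these results separately from the six-month score. The cost is one early use of the planned tests per removal. The early result does not replace the lost six-month score.

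Neither change adds a visit for subjects who stay on drug. No change to the LDL rules in Tables 1 and 2 is proposed.
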